8.2.4 Revised Fibromyalgia Impact Questionnaire (FIQR)

The FIQR is made up of 3 domains: (1) functional (9 questions); (2) overall impact (2 questions) and (3) symptoms (10 questions). If 2 or more items are missing from the functional domain, the domain will be considered invalid for that visit. Likewise, if *any* item is missing from the overall impact domain or the symptom domain, those domains will be considered invalid.

To account for missing items in the functional domain, the score will be recalculated as:

$$\text{New score} = (\text{Raw score} / \# \text{ of items answered}) \times \# \text{ of items in domain}$$

The FIQR total score can be determined after all domain scores have been calculated using the following steps. First, divide the function domain score by 3, divide the overall impact domain score by 1, and divide the symptom domain score by 2. Next, add the three resulting domain scores to obtain the total score of FIQR. If any domain score is missing, then the total is missing.

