 - a. Results of the C-SSRS and BDI-II should be reviewed together at each visit to ensure (1) the patient is not experiencing suicidal ideation or worsening depression that requires intervention and (2) both scales are providing a consistent clinical picture of the patient with regard to suicidality. (Telephone visit exception – response to Question #9 of the BDI-II is reviewed with the patient and C-SSRS is administered over the phone).
- Assess occurrence of adverse events
- Have patient complete all PROs: (Telephone visit exception – all PROs should be mailed ahead of the visit and returned to the clinic after completion via courier):

- a. PGIC
 - b. FIQR
 - c. Clinic administered assessment of pain by both 24-hour and weekly recall using 11-point (0-10) NRS scale
 - d. PROMIS scales for sleep disturbance and fatigue
 - e. CSFQ-14 female or male version, as appropriate
- Ensure that all PROs were accurately and fully completed
 - Brief physical examination, including vital signs, weight (Telephone visit exception – brief physical exam, vital signs, and weight are not required)
 - Examination of the oral cavity. Ensure that this exam includes the sublingual area and that any abnormalities are carefully described on the oral exam source document. (Telephone visit exception – visual exam of the oral cavity is not required – but in addition to standard inquiry about AEs, site staff will inquire specifically if there have been any changes or problems in the oral cavity. Patients reporting any concerning lesion description or painful processes in the oral cavity possibly related to study drug exposure should be strongly urged to come into the clinic for an Unscheduled Visit for oral cavity exam. In circumstances in which, due to the COVID-19 pandemic it is not possible for the patient to return to the clinic for the Unscheduled Visit exam, a clinician certified by the Sponsor to conduct oral cavity examination should contact the patient by phone and obtain greater history and description of the oral cavity AE by patient, potentially augmented with images of oral cavity taken by the patient and sent to the site for the examining clinician to *textually* document in the oral exam source document.)
 - Obtain blood for clinical laboratory tests (Telephone visit exception – laboratory tests are not required).

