8.2.5 Patient Reported Outcomes Measurement System (PROMIS) Instruments

8.2.5.1 PROMIS Short-Form (SF) Fatigue and Sleep Disturbance Instruments

The PROMIS Short-Form Fatigue and Sleep Disturbance Instruments each consist of 8 items in which responses are scored 1 to 5 for each item. Scores for all items are totaled to create a raw score. Either instrument will be considered invalid if 50% of the items are missing. If more than 50% of the items are answered, the raw total score will use the following formula to determine a new calculated score to account for missing items.

$$\text{New raw score} = (\text{Raw score} / \# \text{ of items answered}) \times \# \text{ of total items}$$

New raw scores that are fractions are rounded up to the nearest whole number. Once a new raw score has been calculated, a T-score will be determined using [Appendix A](#) for Fatigue Inventory and [Appendix B](#) for Sleep Disturbance. The T-scores will be analyzed.

Note that items 1, 2, and 8 of the PROMIS Sleep Disturbance Instrument will need to have their directionality reversed for calculating the totals.

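### One blank item out of ten invalidates the FIQR symptoms score, the second key secondary endpoint, although the SAP prorates the shorter FIQR function and PROMIS scales

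*SAP*

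**What the plan says.** SAP 8.2.4 sets the item-level rules for the FIQR, which has 9 function items, 2 overall impact items and 10 symptoms items.

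- Symptoms and overall impact: if any "item is missing from the overall impact domain or the symptom domain, those domains will be considered invalid". The word any is italicised.
- Function: "If 2 or more items are missing from the functional domain, the domain will be considered invalid for that visit". One blank is therefore tolerated, and a rescaling formula follows: "To account for missing items in the functional domain, the score will be recalculated as" the raw score divided by the items answered, times the items in the domain.
- FIQR total: missing if any domain score is missing.

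SAP 8.2.5.1 covers the PROMIS forms: "The PROMIS Short-Form Fatigue and Sleep Disturbance Instruments each consist of 8 items". "Either instrument will be considered invalid if 50% of the items are missing", and "If more than 50% of the items are answered, the raw total score will use the following formula", which is the same rescaling.

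SAP 8.1.1.2 places the symptoms score second among the six ordered key secondary endpoints, after PGIC. FIQR function, both PROMIS scores and diary sleep quality come after it, and a failure closes everything later. SAP 8.1.3 multiply imputes missing values of the continuous key secondaries by visit. SAP 10.2 repeats the analysis on observed data only.

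The reference list in SAP 14 has scoring guides for PROMIS and the C-SSRS and a paper for the CSFQ-14. It has none for the FIQR.

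**The concern.** The longest of these scales has the least tolerance for a blank, and the documents do not say why. Proration is least risky where many items remain, so one would expect the 10-item scale to be treated at least as leniently as the 9-item one.

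A single blank discards nine observed answers on a confirmatory endpoint in favour of a model draw, and removes the score from the observed-data repeat. The position is worse at baseline. Protocol Table 2 and section 12.2.3 schedule the FIQR at Visits 2 to 6 only, so the SAP 8.1 baseline definition (last non-missing value before first dose) has no earlier form to fall back on. SAP 8.1.3 states no rule for a missing FIQR baseline. Without that score the patient has neither a change from baseline nor the model covariate.

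Four later tests depend on this endpoint passing, so avoidable loss of precision here is not confined to one result.

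**Working it through.** The plan states no figure for this point, and the sample-size assumptions are redacted. Only the planned size can be checked: 2 x 235 = 470.

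**Blanks tolerated**

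| Scale | Items | Invalid at | Blanks tolerated |
|---|---|---|---|
| FIQR symptoms | 10 | 1 or more | 0 |
| FIQR function | 9 | 2 or more | 1 |
| PROMIS (each) | 8 | 4 or more (50% of 8) | 3 |

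**Share of returned forms invalid.** Let p be the chance that an item is left blank, independently across items. The documents do not give p; 0.2%, 0.5% and 1% are assumptions.

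- Current rule: 1 − (1 − p)^10
- One-item allowance: 1 − (1 − p)^10 − 10p(1 − p)^9

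At p = 0.5% the current rule gives 1 − 0.995^10 = 4.89%.

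| p | Current rule | One-item allowance | Per arm of 235, current / allowance |
|---|---|---|---|
| 0.2% | 1.98% | 0.018% | 4.7 / 0.04 |
| 0.5% | 4.89% | 0.11% | 11.5 / 0.26 |
| 1% | 9.56% | 0.43% | 22.5 / 1.0 |

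The per-arm counts suppose that all 235 patients return a form. For comparison, the function domain (2 or more of 9 blank) is invalid in 0.09% of forms at p = 0.5% and 0.34% at p = 1%.

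**Effect on an observed-data comparison.** Take an effect with an assumed 90% power at 235 per arm, two-sided 0.05. With a loss L of Week 14 scores, power = Φ(3.2416 x √(1 − L) − 1.96), where 3.2416 = 1.96 + 1.2816. The three losses under the current rule give 89.4%, 88.5% and 86.9%. With the allowance, power stays at 89.9% to 90.0%. If a valid baseline is needed as well, L becomes 1 − (1 − p)^20, which is 3.9%, 9.5% and 18.2%, and power is 88.8%, 86.9% and 83.4%. These figures ignore what the patient's other visits and the imputation recover.

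**How close a prorated score is.** With equal item variances and a common inter-item correlation r (assumed), the 9-item sum correlates with the 10-item sum at (9 + 81r) / √[(9 + 72r)(10 + 90r)]. For r = 0.3, 0.4 and 0.5 this is 0.990, 0.993 and 0.995. The corresponding figure for an imputed score was not computed.

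**When a blank on an Early Termination form affects Week 14.** SAP 8.1.2 assigns Early Termination data to the closest visit, using midpoints. Week 10 is Day 71 and Week 14 is Day 99 (Protocol Table 2), so the midpoint is (71 + 99) / 2 = Day 85. An earlier termination form maps to an earlier visit, and the Week 14 value is then imputed whether or not that form is complete.

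**The case against.** **The rule may be deliberate.** It is explicit, prespecified and emphasised. Domains of one instrument can have different scoring rules, and no FIQR scoring source is cited, so the documents cannot show whether the strict rule follows the instrument. This stands, and the fix allows for it. The SAP still leaves the asymmetry unexplained.

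**A reader might infer that nobody checks the forms where blanks are likeliest.** At telephone visits they are "mailed ahead of the visit and returned to the clinic after completion via courier", and the Early Termination list in Protocol 11.5.2 lacks the completeness-check line that the other visits have. The documents do not support that inference. Protocol 12.2 asks the coordinator to review efficacy responses for completeness with the patient, unless an instrument's instructions forbid it, and makes no exception for Early Termination. The check in 11.3, 11.4 and 11.5.1 carries no telephone exception, although for mailed forms it can be done only by phone or on return. Protocol 17.6 has missing data resolved with the investigator.

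**A reader might also infer that real Week 14 scores of patients who stop for an adverse event or lack of efficacy are routinely replaced by baseline-type draws.** That happens only when termination falls after about Day 85 and a symptoms item is blank. Before then the blank affects only an earlier visit and the values that the Week 14 draw is conditioned on. Sporadic blanks before discontinuation are imputed as missing at random. Where the override occurs, it agrees with the declared estimand (SAP 10.1.1, carried over by 10.2).

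**The size is assumed.** This also stands. If blanks come as whole unreturned forms, the two rules barely differ.

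**Conclusion.** The inconsistency is real. A 10-item confirmatory score is voided by one blank, while the SAP accepts proration of 9-item and 8-item scores, and no reason or source is given. For post-baseline forms, invalid does not mean lost: the patient stays in the main analysis through imputation, and the cost is mainly some precision. At baseline the plan leaves a gap.

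The effect is probably small. The illustration of 2.0% to 9.6% of forms invalid, against 0.02% to 0.4% with a one-item allowance, rests on assumed skip rates of 0.2% to 1% and on independent blanks, which is close to a worst case. The documents do not support a claim that the endpoint is biased, or that the test sequence is seriously endangered. This is a cheap improvement, not a flaw that threatens the trial's conclusions.

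**What to change.** Before unblinding, extend the function-domain rule in SAP 8.2.4 to the symptoms domain: with exactly one item missing, score = (raw score / 9) x 10; with two or more missing, the domain is invalid. Keep the present rule for overall impact, where one blank is half the domain.

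If the instrument's scoring source requires complete items, cite it, keep the strict score as the main one, and run the prorated score as a sensitivity analysis. In either case, report by arm and visit how many symptoms scores are invalid because of item-level blanks, and state how a missing FIQR baseline is handled.

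The scoring change costs one sentence in the SAP and one line of code. Its downside is the assumption that the blank item lies near the patient's own average on the other nine, which the SAP already accepts for function and PROMIS.

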8.2.5 Patient Reported Outcomes Measurement System (PROMIS) Instruments

8.2.5.1 PROMIS Short-Form (SF) Fatigue and Sleep Disturbance Instruments

The PROMIS Short-Form Fatigue and Sleep Disturbance Instruments each consist of 8 items in which responses are scored 1 to 5 for each item. Scores for all items are totaled to create a raw score. Either instrument will be considered invalid if 50% of the items are missing. If more than 50% of the items are answered, the raw total score will use the following formula to determine a new calculated score to account for missing items.

$$\text{New raw score} = (\text{Raw score} / \# \text{ of items answered}) \times \# \text{ of total items}$$

New raw scores that are fractions are rounded up to the nearest whole number. Once a new raw score has been calculated, a T-score will be determined using [Appendix A](#) for Fatigue Inventory and [Appendix B](#) for Sleep Disturbance. The T-scores will be analyzed.

Note that items 1, 2, and 8 of the PROMIS Sleep Disturbance Instrument will need to have their directionality reversed for calculating the totals.

8.2.6 Changes in Sexual Functioning Questionnaire Short-Form (CSFQ-14)

The CSFQ-14 ([Keller et al. 2006](#)) is validated scale with internal reliability designed to allow a patient to self-evaluate his or her sexual behaviors or problems in a number of areas. The CSFQ-14 will be administered at Baseline (Visit 2) and Week 14/ET (Visit 6). It yields a total score, three subscales corresponding to phases of the sexual response cycle (i.e. desire, arousal, orgasm), and five subscales corresponding to important dimensions of sexual functioning. It is considered a useful scale for assessing sexual side effects of medications. For all items, higher scores reflect higher sexual functioning. For 12 of the 14 items, higher sexual functioning corresponds to greater frequency or enjoyment/pleasure (e.g. 1=never to 5 = every day). For two items (item 10, assessing loss of interest after arousal for women and priapism for men, and item 14, assessing painful orgasm), higher sexual functioning corresponds to lower frequency (e.g. 1=every day; 5=never). Items 10 and 14 are included in the total score but not in any subscale scores.

8.3 Safety Endpoints

To handle missing or partial AE and concomitant medication dates, the following rules will be applied.

For partial start dates:

1. If the year is unknown, then do not impute the date but assign a missing value.
2. If the month is unknown, then:
 - a. If the year matches the year of the first dose date, then impute the month and day of the first dose date.
 - b. Otherwise, assign “January.”
3. If the day is unknown, then:
 - a. If the month and year match the month and year of the first dose date, then impute the day of the first dose date.
 - b. Otherwise, assign “01.”

For partial end dates:

1. If the year is unknown, then do not impute the date but assign a missing value.
2. If the month is unknown, then assign “December.”
3. If the day is unknown, then assign the last day of the month.

Adverse events are categorized as pre-treatment adverse events or treatment-emergent adverse events based on the response to the CRF question “Did the AE start prior to the first dose?”

The missing severity of an AE will be imputed to “severe”; the missing relationship to study drug of an AE will be imputed to “possibly related”.

After implementing the rules above, the following strategy will be used to determine whether medications with missing start or stop dates are prior or concomitant medications:

1. If the start date and stop date are both missing, then the most conservative approach is taken and the medication is considered to be a concomitant treatment.
2. If the start date is missing but the stop date is not missing and is after the day of first study dose administration, then the most conservative approach is taken and the medication is considered to be concomitant.
3. If the start date is missing but the stop date is not missing and is on or before the day of first study dose and after the date of signed informed consent, then the medication is considered to be a prior treatment.
4. If the start date is not missing but the stop date is missing, then the most conservative approach is taken and the medication is considered to be concomitant.

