12.3.1. Adverse Events

Patients will be monitored for AEs throughout the study. Any clinically significant abnormal findings at screening should be recorded in medical history. Adverse Events will be recorded after the informed consent is signed. AEs that are spontaneously reported or elicited or observed are to be recorded on the CRF with the date, time of onset, date and time of resolution, severity, seriousness, causality (relationship to study drug), actions required, and outcome. Additional questions will be triggered for AEs involving the oral cavity.

To elicit AEs, non-leading, simple questions with minimal connotations should be used as the initial questions at all evaluation points during the study. Examples of these questions can be:

- How have you felt since your last visit?
- Have you had any health problems since your last visit?

If an AE occurs, the Investigator will institute support and/or treatment as deemed appropriate. If an AE is unresolved on the last day of the study, an effort should be made to follow up until the AE is resolved or stabilized, the patient is lost to follow-up, or there is some other resolution of the event.

There are many symptoms associated with fibromyalgia that can vary in intensity and frequency over time. Only symptoms that worsen or become more frequent, and in the opinion of the patient are outside of their normal experience, should be reported as adverse events.

Additional information regarding definition and reporting requirements for adverse events, serious adverse events, and pregnancies is provided in [Section 14](#).

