14. DEFINITIONS, RECORDING, AND REPORTING OF ADVERSE EVENTS

14.1. Definition of Adverse Events

According to International Conference on Harmonization (ICH) guidance E2A, Clinical Safety Data Management: Definitions and Standards for Expedited Reporting, an AE is any untoward medical occurrence in a patient or clinical investigation subject administered a pharmaceutical product and which is not necessarily required to have a causal relationship with this treatment. An AE can therefore be any unfavorable and unintended sign (including an abnormal laboratory finding, for example), symptom, or disease temporally associated with the use of a medicinal product, whether or not considered related to the medicinal product.

A TEAE is an AE that either commenced following initiation of study treatment or was present prior to study treatment but increased in frequency or severity following initiation of study treatment.

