11.1 Adverse Events

All AEs, TEAEs, and SAEs will be coded using the MedDRA Dictionary Version 22.1.

The collection of adverse events will begin at the time the subject is consented and screened for the study. Treatment-emergent adverse events (TEAEs) are defined as either new onset AEs with an onset at the time of or following the start of treatment, as indicated by a “no” answer to “Did AE start prior to the first dose?”, or a recurrence of an AE (or medical history) present prior to randomization but increasing in severity, frequency or relationship at the time of or following the start of treatment.

An AE summary table will be presented for the following:

- All TEAEs
- TEAEs by severity
- TEAEs leading to study drug discontinuation
- TEAEs by relationship
- SAEs
- Oral cavity TEAEs
- Oral cavity TEAEs by severity

Summaries of incidence rates (frequencies and percentages), of individual AEs by MedDRA SOC and preferred term will be prepared. Such summaries will be displayed for all TEAEs, oral cavity TEAEs, TEAEs by maximum severity, TEAEs by strongest relationship to study drug and post-treatment AEs.

Each subject will be counted only once within each summation level (SOC; preferred term). If a subject experiences more than one TEAE within each summation level, the TEAE with the strongest relationship or the maximum severity, as appropriate, will be included in the summaries of relationship and severity.

In the AE data listings, all AEs will be displayed. AEs that occur prior to randomization will be considered pre-treatment AEs, and will be determined by a “yes” response to the CRF question, “Did the AE start prior to the first dose?” AEs that start on the date of randomization but have a “yes” response to this question will be categorized as pre-treatment AEs. TEAEs will be defined

from the date of randomization and a “no” response to the CRF question, “Did the AE start prior to the first dose?”

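### SAP 8.3 and the last paragraph of SAP 11.1 class AEs by the start-date question alone, contradicting the TEAE definitions, which include pre-existing AEs that worsen on treatment

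*SAP*

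**What the plan says.** Two passages define a TEAE, and both include worsening.

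- Protocol 14.1 covers events that start after treatment begins and also an event that "was present prior to study treatment but increased in frequency or severity following initiation of study treatment".
- The opening of SAP 11.1 covers new-onset events, shown by a *no* to the CRF start question, "or a recurrence of an AE (or medical history) present prior to randomization but increasing in severity, frequency or relationship" once treatment starts.

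Two passages say how the class is assigned, and neither mentions worsening.

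- SAP 8.3: "Adverse events are categorized as pre-treatment adverse events or treatment-emergent adverse events based on the response to the CRF question" on whether the event began before the first dose. Only two classes are offered.
- SAP 11.1, last paragraph: "AEs that occur prior to randomization will be considered pre-treatment AEs, and will be determined by a" *yes* to that question. TEAEs are counted "from the date of randomization and a" *no* to it.

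Events with a pre-dose start will be in the database. Protocol 12.3.1 says "Adverse Events will be recorded after the informed consent is signed", and SAP 11.1 says "The collection of adverse events will begin at the time the subject is consented and screened for the study". AEs are also assessed at the Baseline visit, before study drug is dispensed (Protocol 11.2.2).

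**The concern.** SAP 11.1 contradicts itself, and SAP 8.3 contradicts the protocol. A programmer needs a rule that can be coded, and the single CRF item is the easiest to code. It gives the opposite class from the definition for one kind of event: an AE that begins in screening and worsens after dosing.

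The at-risk window is the screening period, which lasts at least 7 days, normally up to 35, and up to 49 with Medical Monitor approval (SAP 4, Protocol 7.1).

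Safety is the secondary objective, and the AE incidence tables are built largely on TEAEs. An event that worsened until the patient stopped study drug could be missing from the table of TEAEs leading to discontinuation (SAP 11.1.1). The gap also runs against the caution elsewhere in SAP 8.3, where missing severity is set to the worst grade and missing relationship to possibly related. Section 13 of the SAP, on changes from the planned analysis, mentions only the in-clinic pain assessments and does not declare a narrower TEAE definition.

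**Working it through.** No arithmetic applies to the contradiction itself. The check runs three kinds of event through each of the four passages.

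| Passage | Starts after first dose | Starts before, does not worsen | Starts before, worsens after first dose |
|---|---|---|---|
| Protocol 14.1 | TEAE | not TEAE | **TEAE** |
| SAP 11.1, opening definition | TEAE | not TEAE | **TEAE** |
| SAP 8.3 | TEAE | pre-treatment | **pre-treatment** |
| SAP 11.1, last paragraph | TEAE | pre-treatment | **pre-treatment** |

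The passages agree in the first two columns and disagree only in the third.

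**Who falls in the third column.** The event must (a) be recorded as an AE with a start between consent and first dose, (b) worsen on or after first dose, and (c) not be entered again as a new record. Under Protocol 12.3.1, clinically significant abnormal findings at screening go to medical history, and fibromyalgia symptoms become AEs only when they worsen or become more frequent. If either is first recorded as an AE after dosing, the answer should be *no* and the event is counted.

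**Condition (c).** Protocol 12.3.1 lists what is recorded for each AE, including onset, resolution and severity. Neither document tells sites to open a new record when an existing AE worsens.

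**Outputs.** Third-column events drop out of the TEAE tables (overall, by severity, by relationship, oral cavity) and the summary of TEAEs leading to discontinuation. They remain in the listing of all AEs (SAP 11.1), the listing of AEs leading to discontinuation (11.1.1), the oral cavity listing, which includes pre-treatment events (11.1.3), and the SAE summary (11.1.2), which is not limited to TEAEs.

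**Size.** For each arm, the number of patients affected would be

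N × P(pre-dose AE) × P(worsens, given a pre-dose AE) × P(not re-entered, given worsening).

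Only N, planned at 235 per arm, is in the documents. The three probabilities are not, so no result is given.

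**A smaller mismatch.** The SAP speaks of a recurrence and includes an increase in relationship. The protocol requires only that the event was present, and lists frequency and severity. Both cover worsening, but the wording is not the same.

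**The case against.** The strongest reply is that the worsening limb is in the SAP: the opening of 11.1 ties the CRF question only to new-onset events. On that reading, the sentence in 8.3, which follows the partial-date rules, settles onset when dates are incomplete, and the last paragraph of 11.1 settles events that start on the day of randomization. This does not remove the conflict. Both are worded as general rules, and the last paragraph of 11.1 goes beyond same-day events by requiring a *no* for any TEAE.

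The second reply is that CRF completion guidelines, which are not among the documents, may require a new record at worsening. If so, the practical loss would be small. SAP 2 does leave operational detail out, but not where it bears on the planned analysis, and the TEAE tables depend on this point.

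The third reply, that few events are at risk, largely stands. Regular opioid users and chronic or regular benzodiazepine users are not to be considered (Protocol 9.1). Patients who wash out are in general drug-free for 21 days before randomization, so withdrawal events have time to subside. Oral conditions that would interfere with judging administration-site reactions are excluded (Protocol 8.3, criterion 17), and oral abnormalities at Baseline are noted for later comparison (Protocol 11.2.2).

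A reader might infer that the TEAE tables will be biased in favour of the active arm, or that the oral cavity tables will be materially wrong. The documents do not support either. A difference between arms would require that the drug worsens such events and that sites do not re-enter them, and the documents give no data on either.

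**Conclusion.** The contradiction holds. Two general rules in the SAP give a class that the protocol's definition and the SAP's own definition reject. This is a conflict between stated rules, not merely missing detail.

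The consequence is limited to AEs first recorded between consent and first dose that worsen on study drug and are not re-entered. Those events would be absent from the TEAE summaries but visible in the listings and, if serious, in the SAE summary. The number affected and any imbalance between arms cannot be estimated from the documents. The conclusion assumes that the start-question rule is programmed as written and that no instruction outside these documents requires re-entry. The point should be corrected because the remedy is specific and cheap.

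**What to change.** 1. Amend SAP 8.3 and the last paragraph of SAP 11.1 so that an AE is a TEAE if the answer to the start question is *no*, or if it is *yes* and the event increased in severity or frequency on or after the first dose.
2. Decide whether an increase in relationship also qualifies. It is in SAP 11.1 but not in Protocol 14.1. Use the same wording in every place.
3. State one way to identify worsening: either a new AE record at worsening with its own onset date, or a recorded change in severity or frequency on the existing record. If new records are used, their answer is *no*, and the *yes* branch is needed only for events that were not re-entered. If the existing record is used, confirm that the CRF captures the change and its date.
4. For AE records already collected, identify worsening of pre-dose events by a blinded review before unblinding, and document the decisions.

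The cost is SAP wording, one CRF completion instruction, and a small amount of data review and programming.
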